10.0 Setting

FULL PROTOCOL TITLE: Evaluating Contact Lens Optics

All study visits will be conducted at the University of Houston College of Optometry in the investigators' clinical research examination lanes in the J. Davis Armistead Building and The Ocular Surface Institute (TOSI) in the Health 1 Building.

11.0 Risks to Subjects

The risks to the subjects in the study are the same risks found in standard clinical practice. During study procedures, there is the risk of mild ocular discomfort during clinical procedures due to light being shined on the eye (e.g., slit lamp biomicroscopy), by being asked to not blink for a short period of time during a procedure, or through the use of topical ophthalmic diagnostic agents (e.g., sodium fluorescein, 1% tropicamide, 2.5% phenylephrine, topical anesthetic).

Pupil dilation may interfere with subjects' vision for the next few hours and make near work difficult and increase their sensitivity to light. Potential subjects will be examined to ensure that their pupil can be safely dilated. Potential discomfort from these procedures is transient, self-limiting and is no different than what occurs during pupil dilation and contact lens fitting in standard clinical practice.

Contact lenses will be fitted on right eyes as part of this study. All contact lenses are FDA approved. The risks of contact lens wear are no different than if fitted in clinical practice. The potential for contact lens complications (listed below) are minimal because no contact lenses are being dispensed to the subject (all study contact lenses are worn during the study visit only).

The following problems may occur with routine contact lens wear:

- Burning, stinging, and/or itching of the eyes
- Less comfort over time than when the lens was first placed on the eye
- A feeling like there is something in the eye (foreign body, scratched area)
- Reduced vision or temporary loss of vision due to peripheral infiltrates (white blood cells), peripheral corneal ulcers (inflammation of the cornea), microbial keratitis (infection of the cornea), and/or corneal erosion (defects in the corneal surface)
- Local or generalized edema (swelling)
- Corneal staining (defect in the corneal surface)
- Redness
- Tarsal abnormalities (bumps on the inside upper eye lid)
- Iritis (internal inflammation of the eye)
- Conjunctivitis (infection or inflammation of the white part of the eye or under the eyelids)
- Excessive watering, unusual eye secretions, or redness of the eye

FULL PROTOCOL TITLE: Evaluating Contact Lens Optics

- Poor visual acuity
- Blurred vision
- Rainbows or halos around objects
- Sensitivity to light
- Dry eyes may also occur if lenses are worn continuously or for too long a time

Subjects will be instructed that in the event they experience signs or symptoms associated with a potential adverse event during the study visit, they should immediately inform study personnel.

12.0 Potential Benefits to Subjects

There are no direct benefits that subjects are expected to gain from participating in this study. However, the results from this research may increase our understanding of how multifocal contact lens optics affects retinal defocus and visual performance. This information can ultimately lead to a tool to design more effective multifocal contact lens optics for myopia control.

13.0 Withdrawal of Subjects

Participation in the study is voluntary and subjects can withdraw from the study at any time. Subjects may also be withdrawn from the study by study investigators if they have a study-related adverse event that warrants withdrawal from the study or they fail to follow the study instructions.

14.0 Costs/Payments to Subjects

There is no cost to participate in the study and subjects will not be charged for any of the study procedures. Subjects who are eligible to participate and complete the study will receive a \$50 Amazon gift card. Subjects must be eligible and complete all study procedures to receive the gift card. A parking pass will be provided for subjects on the day of their visit.

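### Section 14 withholds the $50 gift card from an eligible subject who stops or is withdrawn because of an adverse event; a one-sentence exception would remove this modest disincentive (minor)

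*Combined protocol and SAP*

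**What the plan says.** Three sections of the protocol bear on this point.

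- **Section 14.0 (Costs/Payments to Subjects)** offers a single $50 gift card and makes it all-or-nothing: "Subjects must be eligible and complete all study procedures to receive the gift card". It mentions no partial payment and no exception. The other benefit has no completion condition: "A parking pass will be provided for subjects on the day of their visit".
- **Section 13.0 (Withdrawal of Subjects)** says that "subjects can withdraw from the study at any time". It adds: "Subjects may also be withdrawn from the study by study investigators if they have a study-related adverse event that warrants withdrawal from the study". Failure to follow instructions is the other ground for withdrawal by an investigator. The section does not mention payment.
- **Section 11.0 (Risks to Subjects)** instructs subjects that "in the event they experience signs or symptoms associated with a potential adverse event during the study visit, they should immediately inform study personnel".

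Section 9.0 (Procedures Involved) lists examiner-performed checks: a slit lamp examination with fluorescein, intraocular pressure, lens fit, and acuity with the lenses. It does not say when the slit lamp and pressure measurements fall relative to lens wear. Its list of what is measured with each lens on the eye is centration, topography, aberrations, acuity and contrast sensitivity.

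**The concern.** Read together, the payment rule works against two other statements in the protocol. Section 11.0 wants symptoms reported immediately, and Section 13.0 makes withdrawal free. Section 14.0 attaches the loss of the whole card to what may follow from either. It treats a subject removed for safety in the same way as one removed for not following instructions.

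What is at stake is subject protection. A subject with a symptomatic eye part-way through a visit of about 2.5 hours has a small financial reason to say nothing and finish. This matters somewhat more here because the protocol states no other route by which an adverse event is to be reported during the visit, and specifies no slit lamp or pressure check while a lens is worn.

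**Working it through.** This is mainly a matter of reading the sections side by side. The plan gives no figure for early withdrawals or adverse events to reproduce, and its sample size of 10 (Section 5.0) does not enter the argument.

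**Inputs.** Card value $50, paid only if the subject is eligible and completes everything (Section 14.0). Parking pass not tied to completion (Section 14.0). Withdrawal by the investigator is discretionary and, on safety grounds, applies "if they have a study-related adverse event that warrants withdrawal from the study" (Section 13.0). Up to 25 enrolled and screened, at least 10 completers wanted (Section 5.0).

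**Step 1: apply Section 14.0 to each course a visit can take.**

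| Course of the visit | Gift card | Parking pass |
|---|---|---|
| Not eligible at screening | $0 | yes |
| Eligible, no symptoms, completes | $50 | yes |
| Eligible, reports symptoms, continues and completes | $50 | yes |
| Eligible, has symptoms, says nothing, completes | $50 | yes |
| Eligible, reports symptoms, withdrawn by the investigator before the end | $0 | yes |
| Eligible, stops by own choice because of symptoms before the end | $0 | yes |

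Reporting by itself costs nothing (third row). The loss arises only in the last two rows, and there it is $50 - $0 = $50, the whole card, at any point before the final procedure.

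**Step 2: look for an exception elsewhere.** Section 13.0 does not mention payment, and neither does the reporting instruction in Section 11.0. No other visible section prorates the card or protects a subject withdrawn for safety. The consent form may address it, but its text was not available for review.

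**Step 3: ask what else would detect an event.** The slit lamp and pressure measurements are planned, but without stated timing. Section 11.0 adds a check that the pupil can be safely dilated, which comes before dilation. The list of measurements for each lens in Section 9.0 includes neither the slit lamp nor pressure. Staff do observe the eye when they check fit and centration. Self-report is thus not the only safety observation in the plan, but it is the only stated instruction for reporting adverse events during the visit.

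**Step 4: price the change.** The extra cost is $50 × k, where k is the number of eligible subjects who stop or are withdrawn because of an adverse event. The documents give no value for k. If exactly 10 of 25 complete and every other subject is such a case, k = 25 - 10 = 15 and the cost is 15 × $50 = $750. That caps the cost only if at least 10 subjects complete; the limit set by enrolment alone is 25 × $50 = $1,250. Both are extremes, because the non-completers will include screening failures, who are unpaid under either rule.

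**The case against.** The strongest reply is that this is a small matter in a low-risk setting. The study is one supervised visit, the lenses are FDA approved and not dispensed, and Section 11.0 describes the discomfort expected from the procedures as mild and transient. A subject who mentions such discomfort and continues is paid in full. Withdrawal by the investigator is discretionary and reserved for events that justify it, and an event of that kind is hard to hide from an examiner working at the eye. The consent form may already state what is paid on early withdrawal. All of this stands, and it is why the point is minor. It does not change what Section 14.0 says, and if the consent form differs, the two need reconciling.

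A reader might infer stronger conclusions that the documents do not support:

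- *That self-report is the only safety information collected.* It is not. Slit lamp, intraocular pressure, lens fit and acuity are also planned.
- *That a withdrawn subject loses everything.* The card is lost; the parking pass is not.
- *That under-reporting is built into the plan.* The incentive is visible in the text, but its effect is not. The documents give no adverse-event rate, no expected number of withdrawals, and no evidence that $50 for a visit of about 2.5 hours changes reporting.
- *That tolerated discomfort would distort the acuity and contrast-sensitivity results.* This is speculation with no size attached, and the outcome behind the sample size is change in peripheral refraction.

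**Conclusion.** The point holds as a minor item. As written, Section 14.0 denies the full $50 to an eligible subject who follows the Section 11.0 instruction that "they should immediately inform study personnel" and who then stops, or is withdrawn under Section 13.0, before the last procedure. That is a stated rule at odds with the protocol's own reporting instruction and free withdrawal, not merely an omitted detail.

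The size is $50 per affected subject, and the number affected is unknown but expected to be small. The conclusion assumes that Section 14.0 is applied literally and that no exception exists in text unavailable for review. Any discouragement of reporting is a reasonable inference from the incentive, not something the documents demonstrate. No endpoint, analysis, sample size or clinical rule is affected.

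**What to change.** Add one sentence to Section 14.0: an eligible subject who stops, or is withdrawn by the investigators, because of an adverse event receives the full gift card. Check the consent form and make its payment paragraph agree.

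The direct cost is $50 per affected subject, plus the administrative effort of a short amendment and, if needed, a revised consent form. Payment for screening failures and for withdrawals unrelated to safety can stay as it is. When and why a subject is withdrawn is untouched; only what is paid afterwards changes.

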15.0 Confidentiality

Subjects will enter their name on the consent form, and their contact information will also be collected for subject scheduling purposes. Identifying information will not be collected on the data collection forms. A unique identification code will be assigned to each subject and used on the data collection forms to identify subjects. The study key linking each subject to their unique identification code will be stored on a password-protected file and will be available only to the study personnel. This key will be stored for 3 years after study completion. All study documents will be securely kept in the investigator's laboratory.

FULL PROTOCOL TITLE: Evaluating Contact Lens Optics

16.0 Provisions to Protect the Privacy Interests of Subjects

Study personnel will discuss the details of the study with potential subjects. This discussion will take place in a quiet and private area, and will take as long as necessary to explain all the details of the study to the understanding of the subject.

17.0 Informed Consent Process

This study will follow the University of Houston Division of Research SOP: Informed Consent Process for Research (HRP-090). The participant will be provided an opportunity to read the informed consent form and to have any questions answered before deciding whether to participate. Should they decide to participate, study personnel will obtain written informed consent from the participant. The consent form will be signed and dated by both the participant and a member of the study personnel who has been approved to obtain consent. The participant will receive a copy of the signed consent documents and the originals will be filed in the subject binder on site in a secure location.

18.0 Process to Document Consent in Writing

The study will follow the University of Houston Division of Research standard operating procedure regarding written documentation of informed consent (SOP: Written Documentation of Consent (HRP-091)). The consent form will be signed and dated by both the study subject and a member of the study personnel who has been approved to obtain consent. The study subject will receive a copy of the signed consent documents and the originals will be filed in the subject binder on site in a secure location. A copy of the informed consent document is included in the study related documents.

19.0 HIPAA

To assess eligibility for participation in the study, demographic information, general medical and eye health information will be collected on the potential subjects by self report. No information will be obtained from or added to any medical record at the University Eye Institute.

20.0 Data Management

Data will be stored both in a paper file and electronically. Paper files will be locked in the research lab, and electronic data will be stored on a password protected computer. Data will be kept for a minimum of 3 years after completion of the project.

Data analyses will be conducted using standard software packages. Descriptive statistics will be conducted to describe the data. Tests of normality will then be conducted followed by appropriate parametric or non-parametric hypothesis testing and correlation analyses.

FULL PROTOCOL TITLE: Evaluating Contact Lens Optics

21.0 Sharing of Results with Subjects

At the end of the study, subjects will be informed of the order in which contact lenses were worn. Results from analysis of the data will not be shared directly with subjects but may be presented at as part of a research talk or published in an academic journal.

22.0 Resources

The study team has completed all necessary requirements for ethical training. [name] OD PhD, has nearly two decades of experience conducting clinical care and research and will oversee all study personnel.

With an abundance of contact lens wearers in the surrounding community, we do not anticipate difficulty identifying eligible subjects. We understand the possibility of slower than normal recruitment due to COVID-19; therefore, we have set an anticipated target of 9 months to complete all visits.

All clinical equipment that will be needed to complete the study are available within the University of Houston College of Optometry.

FULL PROTOCOL TITLE: Evaluating Contact Lens Optics

